2.3 Organ Response-Evaluable Population

The Organ Response-Evaluable population is defined as patients who receive at least 1 cycle of MLN9708, have amyloid involvement of at least kidney or heart at baseline, and have at least 1 postbaseline organ response assessment.

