7.5.12.2 Amyloid-Related Organ Assessments

Amyloid-related organ assessments (see Section 15.7) are to be performed for all patients at screening; after Cycles 3, 6, 9, and 12; every 6 months thereafter until disease progression; and at the End-of-Study visit (as outlined in the [Schedule of Events](#)).

The following procedures/ tests should be included at a minimum to assess amyloid-related organ involvement. If clinically indicated, additional assessments may be performed at the discretion of the investigator. ^(23, 54, 55, 56)

Heart: NT-proBNP, BNP, troponin, echocardiography, physical examination

Kidney: 24-hour urine proteinuria, serum creatinine, eGFR, serum albumin

Liver: alkaline phosphatase, ALT, ultrasound/CT scan/ MRI (as indicated)

Peripheral nervous system: patient reported symptoms, physical examination, electromyography (EMG) (if indicated)

Autonomic nervous system: patient reported symptoms, determination of postural hypotension

Soft tissue: physical examination, imaging as indicated

These assessments include relevant AEs and patient-reported symptoms, physical findings, and special laboratory tests for individual organ sites. In addition, radiographic, CT, MRI,

and ultrasound techniques may be performed as indicated to assess organ involvement. In some cases, tissue sampling may be necessary. Detailed cardiac evaluations are planned. At each staging evaluation, the organ response/improvement will be assessed relative to baseline.

Cardiac Assessments

Cardiac assessments are to be performed for all patients as outlined in the [Schedule of Events](#).

The assessments include, but are not limited to:

- Relevant AEs and clinical findings, such as dyspnea, fluid retention, fatigue
- Cardiac markers (NT-proBNP and troponin T or I)
- Blood pressure
- NYHA classification determination (see Section [15.4](#))
- Echocardiogram at baseline; Cycles 3, 6, 9, and 12; and every 6 months thereafter until disease progression

The following data may be collected: 2D-guided M-Mode (wall thickness and chamber diameters), short-axis, long-axis, apical 4-chamber and 2-chamber video clips (5 beats each), transmitral, transaortic, transtricuspidal, and pulmonary vein Doppler studies, mitral and tricuspidal annulus longitudinal excursion, tissue Doppler imaging for systolic and diastolic wall velocities. Strain and strain rate analyses -may also be analyzed off-line from the short-axis and 4-chamber video clips at the discretion of the investigator.

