8.1.4 Procedures for Handling Missing, Unused, and Spurious Data

All available efficacy and safety data will be included in data listings and tabulations. No imputation of values for missing data will be performed.

Data that are potentially spurious or erroneous will be examined according to standard data management operating procedures.

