2. POPULATIONS FOR ANALYSIS

2.1 Safety Population and Enrolled Patients

The Safety population is defined as patients who receive at least 1 dose of MLN9708. The Safety population will be used for all safety analyses. In this study, the enrolled patients are the patients who received at least 1 dose of MLN9708.

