2.4 Hematological Response Evaluable Population

The Hematologic Response-Evaluable population is defined as patients who receive at least 1 cycle of MLN9708, have measurable disease at baseline, and have at least 1 post-baseline hematologic response assessment.

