5. STATISTICAL METHODOLOGY

Analyses will be primarily descriptive in nature. No formal statistical tests will be performed. Summary tabulations will be presented that display the number of observations, mean, standard deviation, median, minimum, and maximum for continuous variables, and the number and percentage (calculated using nonmissing values) per category for categorical data, unless specified otherwise.

Patients will be analyzed at the dose level to which they were originally assigned, including those who receive subsequent treatment at a lower dose level.

The analyses for the clinical study report (CSR) will be conducted after 75% of patients have PD or 12 months after last patient is enrolled, whichever occurs first in the study. At that time, all relevant data will be queried and cleaned; a database snapshot will be taken and used for the CSR. Additional follow-up treatment data will be entered into the database through study termination. Analyses may be updated based on additional information. An addendum to the CSR may be written if warranted based on these analyses. If deemed appropriate, however, the sponsor may decide to perform the analyses for CSR at the end of the study (EOS), which is approximately 2 years after the last patient is enrolled.

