5.8.1 Efficacy Endpoints

Best overall hematologic response is defined as the best hematologic response over time. It will be calculated and summarized in 2 time frames: (1) Up to the End of Treatment (EOT) visit; and (2) Up to the initiation of alternative antineoplastic therapy or EOS.

Hematologic objective response rate (ORR) is defined as the proportion of patients who achieved a PR or better response as best overall response in the Hematological Response-Evaluable population. Additional hematologic response rates are defined in the following table in the Hematological Response-Evaluable population. All the hematologic response rates will be calculated and summarized in 2 time frames: (1) Up to the EOT visit; and (2) Up to the initiation of alternative antineoplastic therapy or EOS.

Hematologic Response Rate:	Proportion of Patients in the Hematological Response-Evaluable Population Whose Best Overall Responses Are:
CR Rate	CR
VGPR Rate	VGPR
PR Rate	PR
No Change (NC) Rate	No Change (NC)
PD Rate	PD
ORR	PR or VGPR or CR
VGPR or better	VGPR or CR

Vital organ response is defined as the best response of either heart or kidney over time. Organ-specific response is defined as the best response of each defined organ over time. Organ response rate is defined as the proportion of patients who achieved certain response (including response, no change, and PD) in the Organ Response-Evaluable population. Organ-specific response rate will be calculated in the subgroup of the Organ Response-Evaluable population with amyloid involvement of the specific organ at baseline. All the above organ response rates will be calculated and summarized in 2 time frames: (1) Up to the EOT visit; and (2) Up to the initiation of alternative antineoplastic therapy or EOS.

Time to hematologic response is defined as the time from the date of the first dose of MLN9708 to the date of first documentation of a hematologic response (PR or better). Time to vital organ response is defined as the time from the date of the first dose of MLN9708 to

MLN9708**Study C16007 Statistical Analysis Plan**

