5.8.2 Efficacy Analyses

The hematologic response (CR, VGPR, PR, no change [NC], PD) rate will be tabulated and analyzed based on the Hematologic Response-Evaluable population and presented with a 2-sided 95% exact binomial confidence interval. In addition, the overall hematologic response rates up to the end of Cycle 3 and up to the end of Cycle 6 will also be tabulated and analyzed in a similar way.

Vital organ response rate will be tabulated and analyzed based on the Organ Response-Evaluable population. Organ-specific response rate will be tabulated and analyzed based on in the subgroup of the Organ Response-Evaluable population with amyloid involvement of the specific organ at baseline. Estimates of the organ response rate will be presented with 2-sided 95% exact binomial confidence intervals.

MLN9708**Study C16007 Statistical Analysis Plan**

Best hematologic response, time to hematologic response, time to best hematologic response, duration of hematologic response, time to hematologic PD, hematologic PFS, and OS will be presented in a by-patient listing. Vital organ response, organ-specific response, time to vital organ response, duration of vital organ response, time to organ PD, organ PFS, and OS will be presented in a by-patient listing.

Time to hematologic response, time to best hematologic response, duration of hematologic response, time to hematologic PD, hematologic PFS, and OS (1-year OS rate) will be analyzed using standard survival analysis techniques based on Kaplan-Meier estimates, if appropriate.

Raw values of serum M-protein, urine M-protein, serum free light chain (FLC), and the difference between amyloid-forming and nonamyloid-forming free light chain (dFLC), as well as the change from baseline, will be presented in by-patient listings. A waterfall plot will be generated to display the maximum change from baseline in dFLC.

QOL will be assessed for patients in the expansion cohorts only using the European Organisation for Research and Treatment of Cancer Quality of Life Questionnaire-Core 30 (EORTC-QLQ-C30, multiple myeloma module). Descriptive statistics will be presented for both the actual values and the changes from baseline in EORTC-QLQ-C30 assessment over time. EORTC-QLQ-C30 assessments will be analyzed to determine if hematologic response to therapy is accompanied by measurable improvement in QOL.

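### Response rates are planned only in patients with a post-baseline assessment; an all-treated rate should be added, mainly for organ response

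*SAP*

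**What the plan says.** SAP 2.3 admits a patient to the organ response population on three conditions: at least one cycle of MLN9708, heart or kidney involvement at baseline, and that the patient "have at least 1 postbaseline organ response assessment". SAP 2.4 does the same for hematologic response. It replaces organ involvement with measurable disease and requires patients to "have at least 1 post-baseline hematologic response assessment". Protocol 8.1.3 gives matching definitions.

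The rates are computed in these populations only. SAP 5.8.2 states: "Vital organ response rate will be tabulated and analyzed based on the Organ Response-Evaluable population". SAP 5.8.1 defines the hematologic objective response rate as the share of patients with a "PR or better response as best overall response in the Hematological Response-Evaluable population".

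No other rule returns the missing patients to the denominator:

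- SAP 5 reports "the number and percentage (calculated using nonmissing values) per category for categorical data" unless otherwise specified.
- Protocol 8.1.4 says: "No imputation of values for missing data will be performed".
- SAP 2.1 equates the Safety population with the enrolled patients but assigns it to safety work: "The Safety population will be used for all safety analyses".
- SAP 6, on changes from the protocol, adds no response analysis.

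On timing, Protocol 7.5.12.2 schedules on-treatment organ assessments "after Cycles 3, 6, 9, and 12". The Protocol Summary adds one at the End-of-Treatment visit, and Protocol 7.9 requires the End-of-Treatment procedures when study drug is stopped. Hematologic response is assessed in the rest period of every cycle (Protocol 7.5.12.1).

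**The concern.** The post-baseline assessment condition is met or missed after treatment starts, so who is counted can depend on how the patient fares. A patient who dies or is lost before any organ assessment is removed from the organ response rate, not counted as a non-responder. The plan treats the same death as an event in organ and hematologic progression-free survival (SAP 5.8.1), so the two kinds of endpoint handle it differently.

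The exposure is greatest for organ response, because its first scheduled on-treatment look comes after three 28-day cycles, or 12 weeks. For hematologic response the first look comes at the end of Cycle 1.

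Organ response is the quantity on which both expansion cohorts were sized, and those cohorts are meant in part to characterize efficacy. A reader who takes the evaluable rate as the rate among patients given the drug could read it too high. If attrition differs between cohorts, as the planning numbers imply, the naive and exposed rates are also affected unequally.

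**Working it through.** **Inputs** (Protocol 8.1.1 and SAP 5.1)

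- Proteasome inhibitor-naive cohort: 10 enrolled for 8 evaluable, assumed organ response rate 35%, about 83% probability of at least 2 responders.
- Proteasome inhibitor-exposed cohort: 16 enrolled for 14 evaluable, assumed rate 20%, about 80% probability.
- Interval method: two-sided exact binomial, 95% (Protocol 8.1.6, SAP 5.8.2).

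**Step 1. Reproduce the plan's figures.** P(at least 2) = 1 − (1−p)^n − n·p·(1−p)^(n−1).

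- Naive: 1 − 0.65^8 − 8 × 0.35 × 0.65^7 = 0.831, against the stated 83%.
- Exposed: 1 − 0.80^14 − 14 × 0.20 × 0.80^13 = 0.802, against the stated 80%.

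Both reproduce.

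**Step 2. Implied attrition.** The plan gives only the counts; the fractions follow from them.

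- Naive: 1 − 8/10 = 20%.
- Exposed: 1 − 14/16 = 12.5%.

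Inclusion criterion 5 already requires heart or kidney involvement, so the baseline condition should remove hardly any eligible patient. Protocol 4.2 attributes the allowance to dropout. The planned loss is therefore mainly post-baseline.

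**Step 3. All-treated rate, with every non-evaluable patient counted as a non-responder.** All-treated rate = evaluable rate × evaluable / treated.

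- Naive: 0.35 × 8/10 = 28.0%, a shift of 7.0 points; the evaluable rate is 10/8 = 1.25 times the all-treated rate.
- Exposed: 0.20 × 14/16 = 17.5%, a shift of 2.5 points; ratio 16/14 = 1.14.
- Difference between cohorts: 35 − 20 = 15 points among evaluable patients, 28 − 17.5 = 10.5 points among all treated.

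**Step 4. Range.** Realised attrition is unknown. For assumed non-evaluable shares:

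| Non-evaluable share | 35% becomes | 20% becomes |
|---|---|---|
| 5% | 33.3% | 19.0% |
| 10% | 31.5% | 18.0% |
| 20% | 28.0% | 16.0% |
| 30% | 24.5% | 14.0% |

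**Step 5. Compare with the precision.** Illustration with 3 responders per cohort, exact 95% intervals:

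| Cohort | Evaluable | All treated |
|---|---|---|
| Naive | 3/8 = 37.5% (8.5 to 75.5) | 3/10 = 30.0% (6.7 to 65.2) |
| Exposed | 3/14 = 21.4% (4.7 to 50.8) | 3/16 = 18.8% (4.0 to 45.6) |

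In the naive cohort the estimate moves 7.5 points, while the evaluable interval spans 75.5 − 8.5 = 67 points.

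**Step 6. Effect on the sample-size statement.** With n = 10 and p = 0.28, P(at least 2) = 81.7%. With n = 16 and p = 0.175, it is 79.8%. The planning statement barely changes.

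No parallel calculation is possible for hematologic response, because the documents give no attrition figure for it.

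**The case against.** The other side has several good points.

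- **End-of-Treatment visit.** Patients who stop early for toxicity or progression and attend that visit are assessed and stay in the denominator. A reader might infer that all early dropouts vanish, and the documents do not support that. The cover is incomplete, though. A footnote to the Schedule of Events places the visit at least 30 days after the last dose or before subsequent antineoplastic therapy, so a death or loss in that gap is still dropped.
- **One cycle.** A reader might take this condition to mean a completed cycle. The text speaks only of receiving one, and SAP 5.7.2.1 counts a cycle as treated if any quantity of drug was taken. It may exclude almost nobody; the assessment condition carries the point.
- **Who is excluded.** It is tempting to call the excluded patients treatment failures, because Protocol 1.1.1 describes frequent and often sudden cardiac death. That describes the disease in general. This trial excludes Stage III disease, NYHA class III or IV and serious ventricular arrhythmia (Protocol 5.2), and requires an ejection fraction of at least 40% (Protocol 5.1). A patient lost to follow-up has an unknown outcome, and the plan does not break down why 2 of 10 or 2 of 16 would be non-evaluable.
- **Hematologic response.** Assessment every cycle leaves little room for loss. Some exclusions may arise at baseline: entry requires dFLC of at least 40 mg/L, while Protocol 7.5.12.1 and 15.8 call disease measurable from 50 mg/L.
- **Dose selection.** Protocol 6.4 lets efficacy inform the recommended phase 2 dose, so a reader might infer that the expansion-cohort rates drive it. Those cohorts open only after that dose is established.
- **Visibility.** Deaths count in progression-free and overall survival, on-study deaths are listed, disposition tables give population counts, and responses are listed by patient. A careful reader could largely rebuild an all-treated rate. This does not change the rate that is reported.

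**Conclusion.** The point stands as a low-cost improvement. As written, the plan drops any treated patient without a post-baseline assessment from the response rates and offers no all-treated figure beside them. The evaluable rate may therefore overstate response relative to an all-treated rate, mainly for organ response.

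The size rests on two assumptions: that realised attrition matches the planning counts, and that every non-evaluable patient is a non-responder. The second is the extreme case, so 7.0 points (naive) and 2.5 points (exposed) are the largest shifts at that attrition and at the planning response rates. Both are small beside the exact intervals. The size for hematologic response is unknown and probably smaller.

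A reader might go further and infer that the rates are known to be biased upward or that the sample-size justification is wrong. Neither follows. The reasons for non-evaluability are not given, and the stated probabilities are correct for evaluable patients. These are secondary, descriptive endpoints with no formal tests, so no error rate is affected.

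**What to change.** Keep the evaluable-population analysis. Add to SAP 5.8.2, for each expansion cohort:

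1. The organ response rate with exact 95% interval in all treated patients with heart or kidney involvement at baseline, counting those without a post-baseline organ assessment as non-responders.
2. The hematologic response rate with exact 95% interval in all treated patients with measurable disease at baseline, under the same rule. State which dFLC threshold defines measurable disease for this row.
3. The number of treated patients excluded from each evaluable population, with the reason for each (for example death, loss to follow-up, withdrawal, missed End-of-Treatment visit, or baseline condition not met).

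The response data are already planned for collection. The cost is one extra row per response table, a short tabulation of reasons, and a slightly less favourable figure beside the evaluable one.

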2.4 Hematological Response Evaluable Population

The Hematologic Response-Evaluable population is defined as patients who receive at least 1 cycle of MLN9708, have measurable disease at baseline, and have at least 1 post-baseline hematologic response assessment.

2.5 Pharmacokinetic Analysis Population

The PK Analysis population is defined as patients who receive at least 1 dose of MLN9708 and have sufficient MLN2238 concentration-time data and dosing data to permit the calculation of PK parameters.

2.6 Pharmacodynamic Analysis Population

The Pharmacodynamic Analysis population is defined as patients who receive at least 1 dose of MLN9708 and have sufficient whole blood 20S proteasome inhibition-time data to permit the calculation of pharmacodynamic parameters.

2.7 Protocol Deviation

A listing will be generated for major programmable protocol deviations. It will not affect analysis population definitions.

3. HYPOTHESES AND DECISION RULES

Not applicable for a phase 1 study

4. INTERIM ANALYSIS

As this is a phase 1 study, there is not a formal interim analysis. There will be an ongoing review of safety data with the medical monitor and study investigators.

5. STATISTICAL METHODOLOGY

Analyses will be primarily descriptive in nature. No formal statistical tests will be performed. Summary tabulations will be presented that display the number of observations, mean, standard deviation, median, minimum, and maximum for continuous variables, and the number and percentage (calculated using nonmissing values) per category for categorical data, unless specified otherwise.

Patients will be analyzed at the dose level to which they were originally assigned, including those who receive subsequent treatment at a lower dose level.

The analyses for the clinical study report (CSR) will be conducted after 75% of patients have PD or 12 months after last patient is enrolled, whichever occurs first in the study. At that time, all relevant data will be queried and cleaned; a database snapshot will be taken and used for the CSR. Additional follow-up treatment data will be entered into the database through study termination. Analyses may be updated based on additional information. An addendum to the CSR may be written if warranted based on these analyses. If deemed appropriate, however, the sponsor may decide to perform the analyses for CSR at the end of the study (EOS), which is approximately 2 years after the last patient is enrolled.

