6. DESCRIPTION OF TREATMENT

6.1 Study Drug

The study drug will be administered at the Amyloidosis Research and Treatment Center. The treatment schedule for each patient will be provided to the Intensive Care Department at least 1 week before commencing each treatment cycle. The Intensive Care Unit will grant availability on the days of MLN9708 administration, in the event that any adverse events occur that require emergency or intensive care.

All protocol-specific criteria for administration of study drug must be met and documented prior to drug administration. Study drug will be administered only to eligible patients under the supervision of the investigator or identified subinvestigator(s). Patients should be monitored for toxicity as necessary and doses of MLN9708 should be modified as needed to accommodate patient tolerance to treatment; this may include symptomatic treatment, dose interruptions and adjustments of MLN9708 dose. All doses must be taken as outlined in the Schedule of Events. No doses should be missed or delayed during Cycle 1 due to patient scheduling. Following agreement between the investigator and the sponsor, eligible patients may take study drug at home as directed.

Refer to Study Manual for additional instructions regarding study drug administration.

MLN9708 Administration

The study drug should be taken on an empty stomach, at least 1 hour before or no sooner than 2 hours after a meal. The capsules should not be chewed, broken, or opened for administration. Each capsule should be swallowed separately with approximately 240 mL (ie, 8 oz) total of water with the full dose. MLN9708 will be given as a single daily oral dose. The dose will be assigned based on the dose-escalation methodology outlined in [Table 6-1](#). Administration of the capsules may be guided by the dosing tables included in the pharmacy manual.

The prescribed administration of MLN9708 doses in this study is weekly x 3 followed by 1 week without MLN9708 in a 28-day cycle. Missed doses can be taken as soon as the patient remembers as long as the next scheduled dose is 70-72 hours or more away. Patients who vomit after ingestion will not receive an additional dose, but should resume dosing at the time of the next scheduled dose.

Dexamethasone Administration

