6.7 Excluded Concomitant Medications and Procedures

The following medications and procedures are prohibited during the study.

Systemic treatment with any of the following metabolizing enzyme inhibitors is not permitted during this study. The rationale for this is that in the event of a drug-drug interaction with an inhibitor, MLN9708 exposure would be increased leading to a high probability of an AE.

- Strong inhibitors of CYP1A2: fluvoxamine, enoxacin, ciprofloxacin
- Strong inhibitors of CYP3A: clarithromycin, telithromycin, itraconazole, voriconazole, ketoconazole, nefazodone, and posaconazole

Systemic treatment with any of the following metabolizing enzyme inducers should be avoided, unless there is no appropriate alternative medication for the patient's use. The rationale for this (unlike with inhibitors) is that in the event of a drug-drug interaction with an inducer, MLN9708 exposure would be decreased, leading to a reduced chance of toxicity and potentially a reduced chance of efficacy.

- Strong CYP3A inducers: rifampin, rifapentine, rifabutin, carbamazepine, phenytoin, and phenobarbital
- ACE inhibitors (ACE inhibitors should be used with caution and requires consultation with the Millennium clinician. Patients with AL amyloidosis usually poorly tolerate ACE inhibitors, not due to possible interaction with MLN9708, but because of symptomatic hypotension due to an underlying involvement of the autonomic nervous system. Therefore, ACE inhibitors should be excluded in patients with eGFR < 60mg/min/1.72 and in those whom orthostatic systolic blood pressure is < 100 mmHg.)
- Excluded foods and dietary supplements include St. John's wort and Ginkgo biloba
- Warfarin (aspirin is allowed)

The following procedures are prohibited during the study:

- Any antineoplastic treatment with activity against AL amyloidosis, other than study drugs

- Radiation therapy (note that, in general, the requirement for local radiation therapy indicates disease progression)
- Platelet transfusions to help patients meet eligibility criteria are not allowed within 3 days prior to study drug dosing

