8.1.3 Populations for Analysis

The populations used for analysis will include the following:

Safety Population: Patients who receive at least 1 dose of MLN9708. The safety population will be used for safety analyses.

DLT-evaluable Population: Patients who receive all Cycle 1 doses of MLN9708 or experience a DLT in Cycle 1. The DLT-evaluable population will be used to determine the MTD.

Organ Response-Evaluable Population: The organ response-evaluable population is defined

as patients who receive at least 1 cycle of MLN9708, have amyloid involvement of at least kidney or heart at baseline, and at least 1 post-baseline organ response assessment.

Hematologic Response-Evaluable Population: The hematologic response-evaluable population is defined as patients who receive at least 1 cycle of MLN9708, have measurable disease at baseline, and at least 1 post-baseline hematologic response assessment.

Plasma PK Analysis Population: Patients who:

- a. Receive full doses of MLN9708 during Cycle 1 without dose reduction or interruptions through the completion of PK sampling
- b. Do not receive any excluded concomitant medications
- c. Have sufficient plasma MLN2238 concentration-time data to permit reliable estimation of plasma PK parameters

Pharmacodynamic Analysis Population: Patients who:

- a. Receive full doses of MLN9708 during Cycle 1 without dose reduction or interruptions
- b. Do not receive any excluded concomitant medications through the completion of pharmacodynamic sampling
- c. Have sufficient whole blood 20S proteasome inhibition-time data to permit reliable estimation of pharmacodynamic parameters

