5.9.1.2 Plasma and Whole Blood Pharmacokinetic Parameters

The following PK parameters will be calculated by noncompartmental methods, as data permit, from concentration-time data:

Parameter	Definition	Units
C_{max}	Observed maximum concentration	ng/mL
T_{max}	First time C_{max} is observed	hr
C_{trough}	Observed concentration at the end of a dosing interval	ng/mL
AUC_{tau}	Area under the concentration-time curve, time 0 to end of dosing interval, estimated using the linear-log trapezoidal method	hr*ng/mL
λ_{z}	Terminal disposition phase rate constant	1/hr
$t_{1/2}$	Terminal disposition phase half-life	hr
Rac	Accumulation ratio	unitless

Different PK parameters are to be estimated following dosing on Day 1 and Day 15. For some of the doses, concentration data is collected only on either Day 1 or on Day 15. PK parameters will be calculated accordingly. The PK parameters to be estimated for each day of dosing are as follows:

MLN9708
Study C16007 Statistical Analysis Plan

PK Parameter	Dosing Day	
	1	15
C_{\max}	X	X
T_{\max}	X	X
C_{trough}	X	X
AUC_{tau}	X tau = 168 hr	X tau = 168 hr
λ_{z}		X
$t_{1/2}$		X
Rac		X

Individual patient parameter data will be listed. PK parameters will be summarized (N, mean, standard deviation, CV, geometric mean [as appropriate], median, min, and max) according to dose cohort and dosing cycle and day.

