6. CHANGES TO PLANNED ANALYSES FROM THE PROTOCOL

The definition of the PK-Evaluable population and the Pharmacodynamics-Evaluable population are to be changed to include all treated patients instead of patients receiving full doses during Cycle 1 and to remove the condition of “did not receive any excluded concomitant medications”.

The 2 major organs (heart and kidney) will be called vital organs in the SAP and analyses.

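### The SAP widens the PK and PD populations but keeps grouping by assigned dose, so Day 15 summaries can be distorted, in either direction, by patients with altered Cycle 1 dosing or CYP drugs

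*SAP*

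**What the plan says.** Protocol 8.1.3 sets two conditions for the plasma PK population besides adequate data: "Receive full doses of MLN9708 during Cycle 1 without dose reduction or interruptions through the completion of PK sampling" and "Do not receive any excluded concomitant medications". The PD population has parallel conditions.

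SAP 2.5 replaces these with "patients who receive at least 1 dose of MLN9708 and have sufficient MLN2238 concentration-time data and dosing data". SAP 2.6 does the same for PD. SAP 6 declares the change as one "to include all treated patients instead of patients receiving full doses during Cycle 1" and says that the excluded-medication condition also goes. It gives no reason.

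The grouping rule is in the opening text of SAP 5: "Patients will be analyzed at the dose level to which they were originally assigned". It applies even when a patient is later treated at a lower level, and no exception is made for PK or PD. PK parameters are summarised "according to dose cohort and dosing cycle and day" (SAP 5.9.1.2). Concentrations, inhibition data and PD parameters are handled in the same way (SAP 5.9.1.1, 5.9.2.1, 5.9.2.2). None of these sections groups by dose taken, normalises for dose, flags incomplete dosing or plans a sensitivity summary.

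**The concern.** The protocol's conditions ensured that a Day 15 profile labelled with a dose reflected three doses at that level. Once they are removed, the label and the regimen can differ. The protocol contains several routes to this:

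- Restart after a Cycle 1 DLT is one level lower (Protocol 6.5.1).
- Table 6-2 has a within-cycle withholding rule for low counts on a dosing day other than Day 1.
- On late dosing, Protocol 6.1 says "Missed doses can be taken as soon as the patient remembers", subject to a gap of about 72 hours before the next dose.
- For CYP inhibitors, Protocol 6.7 expects that "MLN9708 exposure would be increased leading to a high probability of an AE". Strong CYP3A inducers are to be avoided rather than barred outright, and are expected to lower exposure.

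PK and PD characterisation is a secondary objective. Protocol 1.6 gives its purpose as learning whether amyloid organ injury alters absorption or disposition, or the disease alters the PD effect. A shift caused by dosing history or a CYP drug could be mistaken for that signal. Day 15 is the only profile taken below the MTD, and those cohorts hold 3 to 6 DLT-evaluable patients.

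**Working it through.** The plan states no figure on this point, so there is none to reproduce. The check sizes the effect of one affected patient.

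**Inputs from the documents.** Doses are on Days 1, 8 and 15. Dose levels are 3.0, 4.0, 5.5 and 7.0 mg (Table 6-1). Terminal half-life is more than 4 days, from IV data (Protocol 1.3.1). Day 1 profiles are taken at the MTD only and Day 15 profiles in all patients (PK sampling table; Protocol 7.5.13). About 26 patients are planned at the MTD/RP2D.

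**Assumptions.** One-compartment linear superposition; half-life *t* of 4, 7 or 10 days; one affected patient per cohort.

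**Formula.** Let r = 2^(-7/*t*), and let d1, d8 and d15 be the doses taken as fractions of the assigned dose. Day 15 AUCtau relative to a full-dose Day 1 AUCtau is d15 + r·d8 + r²·d1. With full dosing this is 1 + r + r². It is also Rac, if Rac is the ratio of the two AUCtau values; the SAP gives no formula.

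| | *t* = 4 d | *t* = 7 d | *t* = 10 d |
|---|---|---|---|
| r; r² | 0.297; 0.088 | 0.500; 0.250 | 0.616; 0.379 |
| Full dosing | 1.386 | 1.750 | 1.995 |
| Day 8 missed: 1 + r² | 1.088 | 1.250 | 1.379 |
| Ratio to full | 0.785 (-21%) | 0.714 (-29%) | 0.691 (-31%) |
| Day 8 missed, Day 15 at 4.0 instead of 5.5 mg: 4/5.5 + r² | 0.816 | 0.977 | 1.106 |
| Ratio to full | 0.589 (-41%) | 0.558 (-44%) | 0.555 (-45%) |

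**Late dose.** If the Day 8 dose is taken 3 days before Day 15, r·d8 becomes 2^(-3/*t*):

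- *t* = 4: (1 + 0.595 + 0.088)/1.386 = 1.21, or +21%.
- *t* = 7: (1 + 0.743 + 0.250)/1.750 = 1.14, or +14%.
- *t* = 10: (1 + 0.812 + 0.379)/1.995 = 1.10, or +10%.

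**Cohort effect.** With 1 of n affected, the geometric mean shifts by ratio^(1/n) - 1.

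| | 1 of 6 | 1 of 26 |
|---|---|---|
| Day 8 missed | -3.9% to -6.0% | -0.9% to -1.4% |
| Day 8 missed, Day 15 one level lower | -8.5% to -9.4% | -2.0% to -2.2% |

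**CYP drugs.** The documents give the direction but not the size. Assuming a 1.5- to 3-fold rise with an inhibitor, 1 of 6 gives 1.5^(1/6) - 1 = +7% to 3^(1/6) - 1 = +20%. Assuming a fall to 0.5 or 0.25 of normal with an inducer, 1 of 6 gives -11% to -21%.

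**The case against.** The strongest reply is that affected Cycle 1 profiles will be rare.

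- Protocol 6.5.1 allows dose modification in Cycle 1 only after a DLT, and Protocol 4.1 directs holds and reductions under Section 6.6 to Cycle 2 onward, when no PK is drawn. Table 6-2 carries no cycle limit, so these passages must be reconciled.
- Protocol 6.1 says that Cycle 1 doses should not be missed or delayed for scheduling reasons.
- A reduced Day 15 profile needs a DLT, recovery and a restart by Day 15.
- Strong inhibitors are not permitted, and exclusion criterion 13 bars the listed inhibitors and inducers for 14 days before first dose.

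All of this stands as an argument about frequency. It does not supply the missing rule.

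The SAP's own safeguards are partial. Anomalous concentrations may be excluded with justification, but a valid concentration after a lower, missed or late dose is not anomalous. SAP 2.7 says the deviation listing leaves the populations unchanged. Individual listings let a reader find affected patients but leave the summaries as they are.

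Two further replies also stand. Escalation is driven by DLTs, and PK is not among the RP2D inputs named in Protocol 6.4, although that list is open. The percentages come from a simple model, whereas the protocol describes three-compartment disposition.

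A reader might infer that one affected patient makes up a third of a cohort mean. That mostly fails: one DLT in 3 expands the cohort to 6 (Protocol 6.4), and a patient missing Cycle 1 doses for other reasons is replaced (Protocol 6.3.1), giving at least 4. One of 3 remains possible for a late dose or a CYP-drug user, or if escalation stops on two early DLTs.

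**Conclusion.** The gap is real: a declared widening of the populations is combined with an assigned-dose rule that suits safety and efficacy but can mislabel exposure. Its consequence is conditional. It needs an affected patient with sufficient data, and then matters mainly in a small cohort: about -4% to -6% on the Day 15 geometric mean AUCtau for a missed Day 8 dose in 1 of 6, up to about -9% with a one-level reduction as well, and about -1% to -2% in a pooled group of 26. These sizes rest on the one-compartment model, the assumed half-lives and one affected patient. The documents do not say how many to expect.

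Three stronger readings are not supported:

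- The dose-cohort summaries are not wrong as they stand. With no affected patients the distortion is zero.
- Accumulation is not at risk across all dose cohorts. Rac needs Day 1 samples, which exist only at the MTD, the largest planned group.
- The bias is not one-way towards low exposure in the least tolerant patients. Late doses and inhibitors raise exposure. Nor does the SAP plan a dose-proportionality analysis that could be flattened.

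The change is also disclosed in SAP 6. What is missing is a reason and a safeguard.

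**What to change.** In SAP 5.9:

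1. State an exception to the assigned-dose rule. Noncompartmental PK/PD summaries and mean plots should be grouped by the dose actually taken on the sampled day, or dose-normalised where a parameter allows it. This deals with reduced doses but not with missed or late ones.
2. Flag profiles with a missed, reduced or late Cycle 1 dose, or with a Section 6.7 CYP inhibitor or inducer. Define how late counts as late, and list the drugs that trigger the flag.
3. Add a sensitivity summary of Day 15 parameters, and of Rac at the MTD, in the Protocol 8.1.3 population.
4. Give the reason for the wider population in SAP 6.

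The wider population stays for listings and population PK. Requiring complete dosing in the main tables would partly undo a deliberate sponsor choice, so that restriction is better placed in the sensitivity summary.

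The cost is SAP wording, a few flags derived from dosing and concomitant-medication data already collected, and one extra table set. Some sensitivity cells will have a slightly smaller N.
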